1.0 Objectives

1.1 Study Objectives

We propose to examine the potential effects of the Frequen-ZZZ/Sleepergize sleep pad – a noninvasive, unobtrusive appliance that generates a magnetic gradient, and that is used on the bed – on multiple sleep outcomes in an 8-week randomized crossover study, and to calculate the effect sizes of the intervention to inform power and sample size for future studies.

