2.0 Background

2.1 Study Rationale

Studying the relationship between sleep and health is important to understand how we might optimize sleep to the benefit of our overall mental and physical well-being.

Normal healthy sleep is generally categorized as the absence of sleep disturbances and disorders, but it also involves obtaining sufficient duration, good quality, and appropriate timing. Insufficient or poor sleep results in a greater risk for adverse health outcomes and complication, and also has been associated with increased mortality rates and diminished quality of life. Therefore, sleep is associated with overall well-being and is necessary for health maintenance. This pilot intervention is expected to provide evidence for the feasibility and efficacy of a sleep-enhancing intervention that generates and systematically applies magnetic field potentials to a sleeper's environment. The exact mechanism of this intervention is not yet understood.

Insufficient sleep, as well as the negative affect and perceived stress that tend to co-occur with poor sleep, have all been linked with higher levels of peripheral inflammation^{12,13}. A preponderance of work investigating links between sleep and inflammation is focused on adverse effects of sleep *disruption*; here, we hope to focus on whether changes can be effected by sleep *improvement*, and specifically by sleep improvement via this unique intervention type (non-invasive, unobtrusive electromagnetic field potential).

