4.2 Recruitment process

4.2.1 How potential subjects will be recruited.

A link to complete the screening (which includes a Screening Consent Form, please refer to CATS attachments) in REDCap will be included in study promotions where feasible. IRB-approved recruitment materials/messages will include contact information (e.g. phone and email) of study staff, which interested parties may use to communicate with members of our research team and inquire about this study. A study-dedicated PSU email account that is password-protected with 2-factor authentication ([contact]) will be established for use in such communications.

Social media accounts dedicated to this research may be created for recruitment, and researchers will also have the option to re-post/share/tweet/forward and otherwise promote advertising post(s) from their own personal social media accounts. Advertising post(s) will be consistent with approved electronic recruitment language (please refer to CATS attachment, "Electronic Recruitment Language") and flyers.

Interested individuals are directed to complete electronic screening in REDCap and, if eligible, to provide their contact information for use in scheduling an appointment for completing in-person screening qualification activities and Informed Research Consent at a later time.

4.2.2 Where potential subjects will be recruited.

Potential participants will be recruited electronically (email, ListServs, social media), in the location(s) of posted flyers (local to the PSU-UP campus), by word-of-mouth, and/or directly (e.g., email); none of these recruitment avenues are bound to a particular physical location.

Study volunteers may encounter the individual contact information of study team members inadvertently elsewhere (e.g., on the university profile pages). In instances of potential volunteers or participants contacting study team members outside the designated email account, those individuals will be redirected to use the dedicated study email account for study-related messaging.

4.2.3 When potential subjects will be recruited.

Potential participants will be recruited as soon as feasible after IRB approval. Recruitment will continue until the target sample size (n=10) reaches randomization. Participant dropout prior to study completion will warrant recruitment of replacement participants up to the target.

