7.0 Number of Subjects and Statistical Plan

7.1 Number of Subjects

We expect to evaluate up to 35 participants in screening qualification, aiming to initially identify up to 20 eligible individuals according to the screening procedures. Screening evaluations will pause at that time by pausing both the REDCap survey availability and by our otherwise manual control of release of the screening survey REDCap link until it is determined by Investigators that additional recruitment is necessary (e.g. to replace participant drop-outs or if failure to identify 20 eligible individuals occurs). Should recruitment need to be re-opened beyond 35 participants an IRB Protocol modification would occur, expecting to regulate future screening qualification in specific intervals to reduce risk of unnecessary screening of individuals. We aim to complete 10 subjects in this study.

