7.2 Sample Size Determination

This pilot study is being used to determine feasibility and effect sizes, therefore no information is available upon which to estimate a minimum necessary sample size. This study will inform the sample size of future studies and proposals.

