7.3 Statistical or Analytic Methods

Primary and secondary outcomes will be compared between sleep pad conditions, within participants, as a change score relative to their own Baseline.

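### Does a 10-person pilot that is meant to supply effect sizes need a defined effect size, an interval and a precision statement written into its plan?

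*Combined protocol and SAP*

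**What the plan says.** All references are to the combined protocol and SAP.

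- **Purpose.** Section 1.1 includes the aim "to calculate the effect sizes of the intervention to inform power and sample size for future studies". Section 7.2 says "This pilot study is being used to determine feasibility and effect sizes" and adds "This study will inform the sample size of future studies and proposals". The background (section 2.1) says "This pilot intervention is expected to provide evidence for the feasibility and efficacy of a sleep-enhancing intervention".
- **Size.** Section 7.1: "We aim to complete 10 subjects in this study". Section 4.2.3: "Recruitment will continue until the target sample size (n=10) reaches randomization", and "Participant dropout prior to study completion will warrant recruitment of replacement participants up to the target". Section 7.2 explains that there was no prior information from which to derive a minimum number.
- **Analysis.** Section 7.3 in full: "Primary and secondary outcomes will be compared between sleep pad conditions, within participants, as a change score relative to their own Baseline".

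The documents state no significance level, hypothesis test, power, success criterion, confidence level or target precision.

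**The concern.** The main numerical product of this pilot is a set of effect sizes, yet section 7.3 does not say what an effect size is. It could be in outcome units or standardised. If standardised, the divisor could be the SD of the paired difference, the between-person SD or the SD of change from baseline. No interval is promised.

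Section 7.2 gives lack of prior data as the reason for having no sample size calculation. That reason does not cover precision: the half-width in SD units depends only on the number of pairs and the confidence level.

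The background also speaks of efficacy where section 7.2 speaks of effect sizes, so the plan can seem to promise more than 10 people can show. If a bare point estimate were reported, a later planner could not see how uncertain it was or which design it suited, and a large or a null result could be over-read.

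**Working it through.** **Inputs.** n = 10 complete pairs (sections 4.2.3 and 7.1); two orders with equal allocation intended (section 6.4.3); contrast from section 7.3. The two-sided 95% level, 80% power for a later trial and roughly normal differences are assumptions. The plan states no precision or power, so there is no figure of its own to reproduce.

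**1. What the stated contrast is.** For one participant with active value A, sham value S and baseline B, the difference between the two change scores is (A - B) - (S - B) = A - S. Baseline cancels. The numerator of any effect size is therefore already fixed in outline: the mean within-participant active-minus-sham difference. Only the divisor is open.

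**2. Precision of the mean difference,** in units of the observed SD of the paired difference:

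- Paired analysis: t(0.975, 9)/√10 = 2.262/3.162 = 0.715.
- With a period term, 5 per order: t(0.975, 8)/√10 = 2.306/3.162 = 0.729.
- With a period term, 6 and 4: 2.306 × √((1/6 + 1/4)/4) = 0.744.
- With only 8 usable pairs, no period term: 0.836.

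In true-SD units the expected half-width is slightly smaller, because a sample SD from 10 values averages 0.973 of the true SD: 0.715 × 0.973 = 0.70.

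**3. Precision of the standardised effect.** This is a different interval. Noncentral-t limits for the standardised paired effect (dz) at n = 10:

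| Observed dz | 95% interval | Half the width |
|---|---|---|
| 0 | -0.62 to 0.62 | 0.62 |
| 0.5 | -0.17 to 1.15 | 0.66 |
| 0.8 | 0.07 to 1.50 | 0.72 |

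So 0.72 describes the mean difference. For the standardised effect the half-width depends on the effect itself.

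**4. Precision of the SD.** √(9/χ²) with 9 degrees of freedom gives 0.69 to 1.83 times the observed SD.

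**5. What this means for a later sample size.** If the next trial were also a crossover with 80% power, an observed dz of 0.5 implies 34 participants. The upper limit of 1.15 implies 9, and the lower limit, being below zero, implies no finite number.

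**6. Whether the missing detail loses anything.** Each participant contributes A and S for each outcome. From the 10 pairs one can compute the mean difference, the SD of the difference, the SD under each condition and the correlation between conditions. With equal SDs and correlation r, the effect in between-person SD units is dz × √(2(1 - r)). At dz = 0.5 this gives 0.50, 0.39 and 0.22 for assumed r of 0.5, 0.7 and 0.9. An analyst can therefore report every version of the effect size, with intervals, from the planned data. Changing the divisor rescales the estimate but not its direction.

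**7. Whether sections 2.1 and 7.2 conflict.** An active-versus-sham effect size is evidence about efficacy, however imprecise. Section 2.1 is background and promises no confirmatory test, and the objective in section 1.1 is to examine potential effects. The two statements are compatible.

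**The case for a change.** The strongest case for a change is that effect sizes are a stated objective, and a plan should define its objective before the blind is lifted. The choice of measure matters. Under the assumptions in step 6, a reported effect size of 0.5 with no named divisor could lead to 64, 106 or 315 per group in a later parallel trial at r of 0.5, 0.7 or 0.9, roughly a five-fold range. Power of 14%, 29% and 62% at true dz of 0.3, 0.5 and 0.8, and the fact that p < 0.05 needs an observed dz of at least 0.72, show how easily a result could mislead. The remedy would be a few sentences and no new data.

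Part of this stands. Section 7.3 does not name a measure or an interval, and an unlabelled effect size would be a poor handover.

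The rest does not carry the point. The power and p-value figures describe a test that the plan does not contain, and the parallel-trial figures describe a future design that it does not mention. The harm requires someone to publish or use an unlabelled point estimate, which the documents nowhere propose. Reporting the mean paired difference, its SD and a 95% interval is ordinary practice for a crossover, and nothing in section 7.3 prevents it. A stated half-width would describe the design without altering it: 10 completers give the same precision whether or not section 7.2 says so. Rewording section 2.1 would change no result.

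**Conclusion.** The description of the gap is accurate, but no change to the plan is needed. Section 7.3 fixes the contrast, the planned data contain everything needed for any sensible effect size and its interval, and the plan makes no power, precision or significance claim that 10 participants fail to meet. An openly labelled pilot with no power basis is a fair choice.

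The size of the uncertainty is worth keeping in mind when the results are read: a 95% half-width of about 0.72 observed SDs of the paired difference (0.73 with a period term), an interval of -0.17 to 1.15 around an observed dz of 0.5, and an SD known only to within 0.69 to 1.83 times its estimate. These figures assume 10 complete pairs, a two-sided 95% level and roughly normal differences; the 0.73 also assumes 5 per order. The view would differ if the plan committed to using the point estimate alone, or to a formal efficacy test. It does neither.

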1.2 Primary Study Endpoints

Primary outcomes include changes in:

- -slow-wave sleep (e.g., stage N3 quantity, proportion, & power-spectral features)
- -sleep duration
- -sleep onset latency
- -sleep quality (e.g., frequency and duration of awakenings; sleep stage entropy measures)
- -insomnia symptoms (e.g. self-reports on the Insomnia Severity Index [ISI])

1.3 Secondary Study Endpoints

Secondary outcomes include changes in:

- -other sleep stages (e.g. N1, N2, REM; quantity, proportion, & power-spectral features)
- -spindle characteristics (e.g., count, stage distribution, power-spectral features)
- -other subjective outcomes
- -inflammatory biomarkers

Exploratory outcomes are changes in pain intensity, pain-related functional interference, and dream content valence.

Additional data to be collected:

These are not considered "Endpoints" because we are not planning an analysis that compares groups based on the following criteria. This information is collected at the Consent visit (#1):

- -Demographics: Although this is a small pilot study, demographic questions are relevant to characterize the overall participant sample when reporting data. This information is for the purpose of recognizing potential limitations of our recruited study group (e.g. our ability to extend the results to other groups). These items ("SES Survey" in CATS) were inspired based on the NIH-NIA CROMS system template for clinical trials and standard NIH-funded race/ethnicity questionnaire ("Race and Ethnicity Survey") with some adjustments (for example: included is an income question to reflect the overall sample's financial SES for this small sample size study, selected rather than the income amount brackets otherwise typically included in similar surveys for larger studies).
- -Health History: This survey includes items considered by the Investigators to be minimally sufficient context for interpreting a particular participant's sleep data and the potential relatedness of study events to the intervention. Some responses also prompt consenting team members to ask relevant probing questions that assess participant readiness for participation/scheduling. This also includes potentially relevant sleeping behavior covariates for exploration, such as sleeping position.

2.0 Background

2.1 Study Rationale

Studying the relationship between sleep and health is important to understand how we might optimize sleep to the benefit of our overall mental and physical well-being.

Normal healthy sleep is generally categorized as the absence of sleep disturbances and disorders, but it also involves obtaining sufficient duration, good quality, and appropriate timing. Insufficient or poor sleep results in a greater risk for adverse health outcomes and complication, and also has been associated with increased mortality rates and diminished quality of life. Therefore, sleep is associated with overall well-being and is necessary for health maintenance. This pilot intervention is expected to provide evidence for the feasibility and efficacy of a sleep-enhancing intervention that generates and systematically applies magnetic field potentials to a sleeper's environment. The exact mechanism of this intervention is not yet understood.

Insufficient sleep, as well as the negative affect and perceived stress that tend to co-occur with poor sleep, have all been linked with higher levels of peripheral inflammation^{12,13}. A preponderance of work investigating links between sleep and inflammation is focused on adverse effects of sleep *disruption*; here, we hope to focus on whether changes can be effected by sleep *improvement*, and specifically by sleep improvement via this unique intervention type (non-invasive, unobtrusive electromagnetic field potential).

3.0 Inclusion and Exclusion Criteria

3.1 Inclusion Criteria

- 1. Written informed consent is obtained from the subject.
- 2. Subject is an English speaker and reader. They are able to understand the procedures related to the study.
- 3. Subject is 40-65 years of age at enrollment
 - a. By self-report at Screening & verified with photo ID at full Consent
- 4. Subject is not engaged in rotating or nocturnal shift employment
 - a. By self-report at Screening
- 5. Subject is living independently
 - a. By self-report and/or according to their status at a community living facility
- 6. Subject's personal residence is equipped with functional WiFi and subject is willing to permit study device connection to their WiFi
 - a. By self-report at Screening
- 7. Insomnia Severity Index score of ≥8 at enrollment
 - a. Based on self-administration at screening
- 8. Willing to refrain from initiating new, sleep-directed interventions (e.g. medication; behavioral) that are not a part of this study protocol for the duration of study participation
 - a. By self-report
- 9. Willing to refrain from all nicotine use for the duration of participation
 - a. By self-report

- 10. Willing to refrain from pet access to the bed or sleeping space for the duration of participation (by self-report)
- 11. Regularly sleeping on a non-water bed
 - a. By self-report
- 12. Has and uses own smart phone or tablet device, and is willing to continue to use personal device daily for study purposes
 - a. By self-report

3.1.1	Does this research involve collecting data from individuals residing outside of the US?	
	No No	
	Yes – identify the countries where data collection will take place	
	Not Applicable	

3.2 Exclusion Criteria

- 1. Diagnosed with a sleep disorder
 - a. By self-report
- 2. Has an implanted medical device (e.g., pacemaker, cochlear)
 - a. By self-report
- 3. Diagnosed serious mental/neurologic health disorder or substance use disorder
 - a. E.g., autism, psychosis, depression/bipolar, dementia
 - b. By self-report
- 4. Personal health history of epilepsy or traumatic brain injury
 - a. By self-report
- 5. Taking any physician-directed pharmacologic intervention for sleep or actively engaged in a clinically-validated course of therapy (including behavioral therapy for sleep)
 - a. By self-report
- 6. Diagnosed with hydration problems, or taking prescribed diuretic medication(s).
 - a. By self-report
- 7. Pregnant, breast-feeding, or planning to become pregnant during the study participation period
 - a. By self-report
- 8. History of negative reaction to acupuncture.
 - a. By self-report
- 9. Recreational use of illicit substances in the past month
 - a. E.g., marijuana, cocaine, amphetamines, depressants, hallucinogens (LSD, PCP, mushrooms), narcotics (heroin/opiates)
 - b. By self-report
- 10. Any nicotine use in the past 3 months
 - a. By self-report
- 11. History of sensitivity to, or considers oneself to be uniquely sensitive to, radiofrequency
 - a. E.g., discomfort when in physical proximity to radio-emitting objects, such as cell towers or modems
 - b. By self-report
- 12. Was previously engaged in this research as a randomized participant
- 13. If a participant does not live within a reasonable commutable distance from the PSU-UP campus (i.e. ~20min) to accommodate off-site study visits, then they must be willing to accept the costs and responsibilities of coming to campus (15-17 visits) in order to participate
 - a. By self-report

3.3 Early Withdrawal of Subjects

3.3.1 Criteria for removal from study

Subjects may withdraw their consent to participate in the study at any time for any reason.

Researchers may withdraw subjects from participation at any time at their discretion, regardless of participant desire to proceed. Reasons for researcher-determined withdrawal of subjects may include:

- 1. Discovery that a participant meets any exclusion criterion
- 2. Subject is unable or unwilling to adhere to protocol requirements, including reasonable scheduling timeline and/or commitments noted in Inclusion Criteria. Specifically:
 - a. Initiating a new, sleep-directed intervention (e.g. medication; behavioral) that is not a part of this study protocol during the course of study participation will warrant withdrawal of subjects by researchers (consistent with Inclusion Criteria). Adherence will be determined by intermittent participant self-report on study surveys.
- 3. Apparent or suspected safety reasons
- 4. Inability of the research team to conduct the protocol (e.g., technical or power failure)

3.3.2 Follow-up for withdrawn subjects

Safety data would be necessary with early withdrawal only in the case of an adverse event. Participants who withdraw from the study prior to completion and who were already randomized at the time of their withdrawal will be offered a survey similar to those completing the study to assess both their awareness of their assigned condition order and so that they have the opportunity to request to be contacted with information about their randomized order after the study concludes (please refer to CATS attachment, "End of Study Survey"). Study participants who withdraw early from the study will also be offered the same optional Follow-Up survey that is offered to completed participants.

Study participants who withdraw early from the study may or may not be eligible to participate again at a later time, depending on the reason for, and timing of, early withdrawal.

There are not any known risks to participants related to truncation of the study intervention (sleep pad use) in excess of those present prior to participation.

4.0 Recruitment Methods

4.1 Identification of subjects

Participants may be identified and recruited directly by several means. Flyers (please refer to CATS attachment) in the Penn State University Park and Centre County region at cooperating businesses/organizations/facilities will be the primary recruitment method, targeting participants in the central-Pennsylvania region. Additional potential recruitment methods include: word of mouth, webbased advertisements (including social media, e-flyers, or similar virtual communications' please refer to CATS attachment "Other Electronic Recruitment"), emails through relevant Penn State University listservs, online participant recruitment platforms (e.g., StudyFinder, ResearchMatch, ActivePALS), news stories about the Investigators' laboratories and their research, and/or direct contact from a repository

of previous research participants who indicated interest in future research participation (using contact information that they provided at that time, please refer to CATS attachment: Direct Recruitment Email").

4.2 Recruitment process

4.2.1 How potential subjects will be recruited.

A link to complete the screening (which includes a Screening Consent Form, please refer to CATS attachments) in REDCap will be included in study promotions where feasible. IRB-approved recruitment materials/messages will include contact information (e.g. phone and email) of study staff, which interested parties may use to communicate with members of our research team and inquire about this study. A study-dedicated PSU email account that is password-protected with 2-factor authentication ([contact]) will be established for use in such communications.

Social media accounts dedicated to this research may be created for recruitment, and researchers will also have the option to re-post/share/tweet/forward and otherwise promote advertising post(s) from their own personal social media accounts. Advertising post(s) will be consistent with approved electronic recruitment language (please refer to CATS attachment, "Electronic Recruitment Language") and flyers.

Interested individuals are directed to complete electronic screening in REDCap and, if eligible, to provide their contact information for use in scheduling an appointment for completing in-person screening qualification activities and Informed Research Consent at a later time.

4.2.2 Where potential subjects will be recruited.

Potential participants will be recruited electronically (email, ListServs, social media), in the location(s) of posted flyers (local to the PSU-UP campus), by word-of-mouth, and/or directly (e.g., email); none of these recruitment avenues are bound to a particular physical location.

Study volunteers may encounter the individual contact information of study team members inadvertently elsewhere (e.g., on the university profile pages). In instances of potential volunteers or participants contacting study team members outside the designated email account, those individuals will be redirected to use the dedicated study email account for study-related messaging.

4.2.3 When potential subjects will be recruited.

Potential participants will be recruited as soon as feasible after IRB approval. Recruitment will continue until the target sample size (n=10) reaches randomization. Participant dropout prior to study completion will warrant recruitment of replacement participants up to the target.

4.2.4	Describe the eligibility screening process. Screening begins when the investigator obtains information about or from a prospective participant in order to determine their eligibility.
	Eligibility screening is occurring before consent* - describe the process below
$\overline{\boxtimes}$	Eligibility screening is occurring after consent - describe the process below
	Eligibility screening is occurring, consent is not being obtained in this research - describe the
pro	ocess below

		Not applicable - Eligibility screening is not being done in this research		
		Consent will occur in 2 phases. Eligibility screening will happen after an electronic Screening Consent Form has been completed by the subject in the REDCap system. Qualification according to Inclusion and Exclusion Criteria will occur as a part of this eligibility screening survey (please refer to "Screening Survey" in CATS attachments). Participants are informed of and agree to scheduling & attending an initial study visit where completion of the Informed Research Consent Form occurs (please refer to "Informed Research Consent" in CATS attachments) and data collection begins. Information from eligibility screening may be used and reported as study data.		
		In some studies, these procedures may not take place unless HIPAA Authorization is obtained OR a waiver of HIPAA Authorization when applicable for the screening procedures is approved by the IRB.		
		*Unless informed consent is waived by the IRB, screening before consent is only permitted when screening activities are limited to the collection of information through oral or written communication OR when identifiable private information or identifiable biospecimens is obtained by accessing records or stored identifiable biospecimens. Screening before consent is not permitted if data will be used for activities other than eligibility screening/recruitment (e.g., data analysis).		
5.0	Consent Process and Documentation			
	5.1	Consent Process:		
		Check all applicable boxes below: Informed consent will be sought and documented with a written consent form [Complete Sections 5.2 and 5.6; If this is the only box checked, mark Sections 5.3, 5.4 and 5.5 as 'Not applicable']		
		Informed consent will be sought but some of the elements of informed consent will be omitted or altered (e.g., deception). [Complete section 5.2, 5.4 and 5.6; If this is the only box checked, mark Section 5.5 as 'Not applicable']		
		Informed consent will not be obtained – request to completely waive the informed consent requirement. [Complete Section 5.5; If this is the only box checked, mark Sections 5.2, 5.3, 5.4 and 5.6 as 'Not applicable']		
	5.2	Obtaining Informed Consent		
